13.4 STATISTICAL ANALYSES

Study Name: Immunogenicity trial of 3 influenza vaccine [VAP3]

Protocol Number: 2021.247

DSRB Ref Number: 2022/00275

Version & date: version 2.0, dated 27 Oct 2022

Page 31 of 38

The stratification variable of vaccination history will be included as a covariate in models for all primary and secondary objectives.

13.4.1 PRIMARY OBJECTIVE

To assess whether vaccination with recombinant quadrivalent influenza vaccine (QIV-R) results in a better antibody response against A(H3N2) viruses than either standard egg-grown vaccine (QIV-E) or cell-based vaccine (QIV-C) as measured by post-vaccination geometric mean titre from the haemagglutination inhibition assay

Post-vaccination GMTs will be calculated for each group using the model described in 13.3, in which the outcome is an individual's post-vaccination titre, estimated given their pre-vaccination titre, prior vaccination status (frequent or infrequent) and the vaccine they were given (QIV-R, QIV-C, QIV-E). A t-test (on a model parameter) will be used to assess statistical significance of the effects of QIV-R versus QIV-E and QIV-C.

13.4.2 SECONDARY OBJECTIVE 1

To estimate whether antibody responses to all 4 vaccine antigens are greatest in participants who received QIV-R and least in participants who received QIV-E, and if this reflects greater cell- to egg-grown antibody titre ratios.

The post-vaccination vs pre-vaccination **log-titre difference** (geometric mean ratio) will be compared using linear regression with the explanatory variable being the type of vaccine (reference QIV-E, separate parameter for QIV-R and QIC-C). A t-test will be used to assess statistical significance of the effects of QIV-R and QIC-C (as compared to reference) as well as the difference in those effects.

The post-vaccination **seropositivity** (coded as 1 if the post-vaccination titre is at least 40, 0 otherwise) will be compared using logistic regression with the explanatory variable being the type of vaccine (reference QIV-E, separate parameter for QIV-R and QIC-C). A t-test will be used to assess statistical significance of the effects of QIV-R and QIC-C (as compared to reference) as well as the difference in those effects.

Seroconversion (coded as 1 if the post/pre vaccination titre ratio is at least 4, 0 otherwise) will be compared using logistic regression with the explanatory variable being the type of vaccine (reference QIV-E, separate parameter for QIV-R and QIC-C). A t-test will be used to assess statistical significance of the effects of QIV-R and QIC-C (as compared to reference) as well as the difference in those effects.

The trend will be determined using the estimate of the effect of the cell vaccine and the estimate of the effect of the recombinant vaccine for each of these outcomes. The expected trend is the cell vaccine producing better outcomes than the egg vaccine (estimate of the effect of the cell vaccine should positive) and the recombinant vaccine producing better outcomes than the cell vaccine (the difference of estimates of the effect of recombinant and cell vaccines should be positive).

13.4.3 SECONDARY OBJECTIVE 2

To estimate whether QIV-R induces antibodies against a greater genetic and antigenic range of A(H3N2) viruses than QIV-C and QIV-E.

The breadth of antibodies induced by vaccination will be measured using pre-vaccination and post-vaccination serum samples tested against a landscape panel of approximately 30 influenza A(H3N2) strains that have circulated since 1968. A metric for response breadth (e.g., the proportion of viruses with post/pre vaccination titre ratio of at least 4) will be calculated for each individual and compared using linear regression as for secondary objective 1.

13.4.4 SECONDARY OBJECTIVE 3

To estimate whether prior vaccination history has less effect on antibody responses induced against all 4 vaccine antigens by QIV-R compared with QIV-C and QIV-E.

All analyses for objective 1 and 2 will be repeated including a covariate to indicate the vaccination history group (0=in frequently vaccination; 1=frequently vaccinated). An interaction term between vaccine received and prior vaccination will be included to allow vaccine effect to vary by history of vaccination. Infrequently vaccinated is defined as 0 or 1 prior vaccinations; frequently vaccinated is defined as 3 or more prior vaccinations with any influenza vaccine.

13.4.5 SECONDARY OBJECTIVE 4

To estimate whether antibody titres against all 4 vaccine antigens are better maintained up to 12months after vaccination with QIV-R compared with QIV-C and QIV-E

Post-season log-titres and seropositivity will be compared the same way post-vaccination log-titres and seropositivity are compared in objective 1.

Post-season response breadth will be using the same methods described for objective 2.

13.4.6 SECONDARY OBJECTIVE 5

To estimate whether QIV-R induces higher frequencies of HA reactive B cells and/or B cells with different HA cross-reactivity profiles and phenotypes compared with QIV-C and QIV-E.

The percentage of B memory phenotype (CD27+ and/or IgD-) cells that are HA probe reactive on d14 will be estimated for each vaccine arm, accounting for pre-vaccination percentage and vaccination history as described in 13.3. The HA probe cross-reactivity, isotype, and phenotype of HA reactive B cells for each vaccine group and time-point will be visually compared using t-distributed stochastic neighbor embedding (t-SNE), a statistical method for visualizing high-dimensional data by giving each datapoint a location in a two or three-dimensional map.

13.4.7 SECONDARY OBJECTIVE 6

To assess whether QIV-R offers better protection against infection compared with QIV-C or QIV-E.

Evidence of influenza infection will be based on RT-PCR-confirmed infection, only, as serological evidence may be biased in vaccinees who elicit a good antibody response to vaccination (22).

Attack rates will be calculated for each vaccination group as the number of cases during the person-time at risk. If there are sufficient cases, the proportion testing positive for each vaccine will be compared using logistic regression with influenza infection as 1 if test-positive and 0 if test-negative or not tested and no ARI. The explanatory variable will be the type of vaccine (1=QIV-R, 2=QIC-C, 3=QIV-E). Samples size permitting, we will also explore whether attack rates were associated with the post-vaccination GMT.

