6 OBJECTIVES AND OUTCOMES

6.1 PRIMARY OBJECTIVE

To assess whether vaccination with recombinant quadrivalent influenza vaccine (QIV-R) results in a better antibody response against A(H3N2) viruses than either standard egg-grown vaccine (QIV-E) or cell-based vaccines (QIV-C) as measured by post-vaccination geometric mean titre from the haemagglutination inhibition assay.

Corresponding outcome measures:

1. Post vaccination GMT in each vaccination group, adjusted for vaccination history and baseline titre.
2. Difference in log-titres between the QIV-R and QIV-E, adjusted for vaccination history and baseline titre.
3. Difference in log-titres between the QIV-R and QIV-C, adjusted for vaccination history and baseline titre.

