6.2 SECONDARY OBJECTIVES

6.2.1 SECONDARY OBJECTIVE 1

To estimate whether antibody responses to all 4 vaccine antigens are greatest in participants who received QIV-R and least in participants who received QIV-E, and if this reflects greater cell- to egg-grown antibody titre ratios.

Corresponding outcomes:

1. Post vaccination trend in GMT QIV-R > QIC-C > QIV-E
2. Post-vaccination seropositivity and trend in seropositivity of QIV-R > QIC-C > QIV-E
3. Pre- to post-vaccine mean fold-rise in GMT (~ Geometric Mean Ratio (GMR)) and trend in fold rise of QIV-R > QIC-C > QIV-E
4. Post-vaccination seroconversion and trend in the proportion who have seroconverted of QIV-R > QIC-C > QIV-E

6.2.2 SECONDARY OBJECTIVE 2

To estimate whether QIV-R induces antibodies against a greater genetic and antigenic range of A(H3N2) viruses than QIV-C and QIV-E.

Corresponding outcomes:

1. Breadth of antibodies induced by vaccination as measured through pre-vaccination, post-vaccination and post-season serum samples tested against a landscape panel of approximately 30 influenza A(H3N2) strains that have circulated since 1968.

6.2.3 SECONDARY OBJECTIVE 3

To estimate whether prior vaccination history has less effect on antibody responses induced against all 4 vaccine antigens by QIV-R compared with QIV-C and QIV-E.

Corresponding outcomes:

For each vaccine type and vaccination history group (frequently versus infrequently vaccinated) compare:

1. Post-vaccination GMT
2. Post-vaccination seropositivity
3. Post-vaccination fold-rise in geometric mean antibody titre (GMT)
4. Post-vaccination seroconversion fraction
5. Post-vaccination antibody breadth (proportion of landscape antigens with GMT>40)

6.2.4 SECONDARY OBJECTIVE 4

To estimate whether antibody titres against all 4 vaccine antigens are better maintained up to 12 months after vaccination with QIV-R compared with QIV-C and QIV-E

Corresponding outcomes:

1. Post-season GMT
2. Post-season seropositivity
3. Proportion of landscape antigens (as per Objective 2) with GMT>40 post-season

6.2.5 SECONDARY OBJECTIVE 5

To estimate whether QIV-R induces higher frequencies of HA reactive B cells and/or B cells with different HA cross-reactivity profiles and phenotypes compared with QIV-C and QIV-E.

Corresponding outcomes:

1. Heterogeneity of antibody generating B cells in terms of phenotype and reactivity against a panel of well-defined recombinant hemagglutinin probes that represent a range of influenza A(H3N2) virus clades.

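### The seropositivity models omit the pre-vaccination titre and so give up about 21–23% of the information on QIV-R versus QIV-E for A(H3N2) at V2

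*Combined protocol and SAP*

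**What the plan says.** Seropositivity is a named outcome of secondary objective 1 (section 6.2.1: "Post-vaccination seropositivity and trend in seropositivity of QIV-R > QIC-C > QIV-E") and appears again under objectives 3 and 4.

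- **13.4.2** sets the outcome to 1 when "the post-vaccination titre is at least 40, 0 otherwise) will be compared using logistic regression with the explanatory variable being the type of vaccine", with QIV-E as reference.
- **13.4** adds one further term to every model: "The stratification variable of vaccination history will be included as a covariate in models for all primary and secondary objectives".
- **13.4.4** reuses the model: "All analyses for objective 1 and 2 will be repeated including a covariate to indicate the vaccination history group", with a vaccine-by-history interaction.
- **13.4.5** reuses it later in follow-up: "Post-season log-titres and seropositivity will be compared the same way post-vaccination log-titres and seropositivity are compared in objective 1".

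Elsewhere the plan does condition on the pre-vaccination value. Section 6.1 defines a primary outcome as "Difference in log-titres between the QIV-R and QIV-E, adjusted for vaccination history and baseline titre". In 13.4.1 the post-vaccination titre is "estimated given their pre-vaccination titre, prior vaccination status (frequent or infrequent) and the vaccine they were given". The B cell analysis in 13.4.6 is done "accounting for pre-vaccination percentage and vaccination history as described in 13.3". Section 8.4 requests a pre-vaccination blood sample from every participant. No reason is given for leaving baseline titre out of the seropositivity model.

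**The concern.** Whether a participant reaches 40 after vaccination depends heavily on the starting titre. Under the 13.3 values the slope on baseline is 0.8 and both the baseline and the error have variance 1. Baseline therefore explains 0.64 / (0.64 + 1) = 39% of the variance of the post-vaccination log-titre within an arm and stratum. A model without it leaves that variation in the noise.

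This is not a question of bias. At stake are the power of the vaccine test and the precision of the difference in seropositivity, in three secondary objectives, for data the trial already holds. The two models also give different odds ratios, so the choice should be fixed before unblinding.

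**Working it through.** **Inputs (13.2, 13.3).** Natural-log scale, since exp(0.5) = 1.65. b0 = 1.1, baseline slope 0.8, prior vaccination −0.2, QIV-C 0.25, QIV-R 0.5, extra QIV-R effect in the frequently vaccinated 0.2, extra QIV-C effect 0. Baseline N(3.7, 1), error N(0, 1). Titres are grouped into doubling intervals, with <10 set to 5. There are 55 evaluable participants per arm per history stratum.

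**The plan's own figure.** Simulating this model and testing b_R at 55 per cell gives power 0.813 one-sided and 0.719 two-sided. The table in 13.3 gives 0.810 and 0.712, so the set-up reproduces.

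**Implied seropositivity at V2.** P(titre ≥ 40) = Φ((mean − ln 40) / √1.64), with ln 40 = 3.689 and √1.64 = 1.281. For QIV-E, infrequently vaccinated, the mean is 1.1 + 0.8 × 3.7 = 4.06, giving Φ(0.290) = 0.614. The other cells follow in the same way (infrequent / frequent): QIV-E 0.614 / 0.553, QIV-C 0.686 / 0.629, QIV-R 0.752 / 0.752.

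**With and without baseline.** 5000 simulated trials at 55 per cell, history in both models. The standardised risk difference is the mean over all participants of the predicted probability under QIV-R minus that under the comparator.

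| | Without baseline | With baseline |
|---|---|---|
| R vs E: log odds ratio | 0.791 | 1.034 |
| R vs E: mean SE | 0.297 | 0.345 |
| R vs E: mean Wald z | 2.646 | 2.979 |
| R vs E: power, one-sided | 0.851 | 0.922 |
| R vs E: power, two-sided | 0.768 | 0.860 |
| R vs E: standardised risk difference | 0.170 | 0.169 |
| SD of that difference | 0.0624 | 0.0548 |
| Mean 95% CI width | 0.243 | 0.213 |
| CI coverage | 0.947 | 0.948 |
| R vs C: power, one-sided | 0.460 | 0.553 |
| R vs C: power, two-sided | 0.341 | 0.423 |

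Both sidednesses are shown because the plan states none for the secondary objectives.

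**Information lost, R vs E.**
- From z: 1 − (2.646 / 2.979)² = 21.1%.
- From the risk difference: 1 − (0.0548 / 0.0624)² = 22.9%.
- Equivalent sample size: 1 / (1 − 0.211) = 1.27 and 1 / (1 − 0.229) = 1.30, so 27–30% more participants.
- A large-sample calculation by numerical quadrature gives 21.9% with grouped baseline titres and 23.0% with ungrouped ones.

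For R vs C the loss is 22.0% from z and 20.3% from the risk difference.

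**Type I error.** With all vaccine effects set to 0, one-sided rejection is 0.049 without baseline and 0.048 with it.

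**Interaction model of 13.4.4 (4000 runs), R vs E.** In the infrequently vaccinated, power goes from 0.464 to 0.565 one-sided and from 0.346 to 0.426 two-sided (risk-difference loss 21%). In the frequently vaccinated it goes from 0.690 to 0.802 and from 0.582 to 0.696 (loss 24%). The interaction test itself stays near 0.11–0.12 one-sided.

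**Sensitivity (assumed values; the plan gives none).**

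| Assumption | Loss, R vs E |
|---|---|
| Slope 0.6, mean post-titre held fixed | 13–15% |
| Slope 0.4, mean post-titre held fixed | 5–8% |
| Slope 0.8, overall seropositivity about 88% | 12–15% (risk difference) |
| Slope 0.8, about 94% | 10% (risk difference) |
| Slope 0.8, about 97.5% | about 3% (risk difference) |
| Strata differ in baseline by 0.5 log units | 21–22% |
| Strata differ in baseline by 1 log unit, total SD 1 | 16–18% |

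**The case against.** The strongest reply is that nothing here is wrong as planned. Randomisation makes the unadjusted test valid. Section 6.2.1 promises no baseline adjustment for seropositivity, and objectives 1, 3 and 4 are worded as estimation with no power target. Unadjusted one-sided power for QIV-R versus QIV-E (0.85) already exceeds the 0.810 of the primary analysis. Adjustment does not make QIV-R versus QIV-C well powered, nor the interaction that objective 3 asks about. The 21–23% also lies near the upper end of the range examined: it needs slope 0.8, mid-range seropositivity and the same baseline distribution in both history strata. Adjustment makes the odds ratio conditional and raises its standard error by 16% (0.345 / 0.297 = 1.16), so a reader looking only at that interval would see it widen.

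All of this is correct as fact, and it limits the point to an efficiency gain on a secondary outcome. It does not remove the point. The covariate is already collected and already used in the primary model. No assumption set examined showed adjustment losing information. Two-sided power at 55 per cell crosses 80% only with it. The wider odds ratio interval reflects a different quantity; on the risk-difference scale, where the target is the same, the interval narrows.

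A further objection also stands. If baseline is added to the fold-rise model, the vaccine coefficients become identical to those of a baseline-adjusted post-titre model with the same other terms, so that analysis would lose its separate meaning.

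**Conclusion.** The concern holds. The seropositivity models in 13.4.2, 13.4.4 and 13.4.5 omit the pre-vaccination titre without a stated reason. Under the plan's own A(H3N2) values this costs about 21–23% of the information on QIV-R versus QIV-E at V2. The figure rests on the slope of 0.8, the seropositivity levels those values imply, and equal baseline distributions in the two history strata. It should not be carried over to the other three antigens or to V3 and V4, where the loss could be anywhere from a few per cent to this size. The unadjusted analysis remains valid and the primary conclusion is untouched. The change is worth making but not essential.

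**What to change.** In 13.4.2, add the pre-vaccination log-titre against the same antigen to the seropositivity logistic model, coded as in 13.3, and carry it into the seropositivity models of 13.4.4 and 13.4.5. Report a standardised risk difference, averaging predictions over all participants, with a named variance method (delta method or bootstrap), beside the odds ratio. State that the odds ratio is conditional on baseline. Make the change before unblinding.

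Leave the breadth metric of 13.4.3 as it is. Adding the covariate to the fold-rise and seroconversion models is optional. The loss there is 5% and 2% at slope 0.8 (about 26% and 15% at an assumed 0.4), and the fold-rise analysis would then duplicate an adjusted titre analysis.

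The cost is SAP wording and one standardisation step, with no new data. The odds ratio changes meaning (log odds ratio about 0.79 to 1.03, with a larger standard error). At about 97.5% seropositivity, delta-method coverage fell to 91–94% with or without the covariate, and at that level some logistic fits separate, so little is gained there.

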13.3 POWER CALCULATIONS

Power calculations were simulation-based. The following model was used for the simulations:

$$\logtitre_{t=2} = b_0 + b_{baseline} \logtitre_{t=1} + b_{priorvax} priorvax + b_C vax_C + b_R vax_R + b_{C-add} vax_C priorvax + b_{R-add} vax_R priorvax + e$$

The following table contains the interpretation of all model terms.

Term	Interpretation
logtitre _{t=2}	Post-vaccination log-titre.
b ₀	Expected post-vaccination log-titre for baseline log-titre 0, infrequent prior vaccination, vaccinated with QIV-E.

b_{baseline}	Expected increase in the post-vaccination log-titre for a 1-unit increase in the pre-vaccination log-titre. Adjusted for prior vaccination frequency and vaccine received.
$\log\text{titre}_{t=1}$	Pre-vaccination log-titre.
b_{priorvax}	Expected difference in the post-vaccination log-titre between the frequently and infrequently vaccinated. Adjusted for baseline titre.
priorvax	0=Infrequent prior vaccinations. 1=Frequent prior vaccinations and vaccine received.
b_C	Expected difference in post-vaccination log-titre between QIV-E and QIV-C. Adjusted for baseline titre and prior vaccination frequency.
vax_C	0=Not vaccinated with QIV-C. 1=Vaccinated with QIV-C.
b_R	Expected difference in post-vaccination log-titre between QIV-E and QIV-R vaccine. Adjusted for baseline titre and prior vaccination frequency.
vax_R	0=Not vaccinated with QIV-R. 1=Vaccinated with QIV-R.
$b_{C\text{-add}}$	Expected additional effect of QIV-C in the frequently vaccinated.
$b_{R\text{-add}}$	Expected additional effect of QIV-R in the frequently vaccinated.
e	Random error

The following table contains the values used for the parameters in the model (subsequent tables will show deviations if there are any).

Term	Value
b_0	1.1
b_{baseline}	0.8
b_{priorvax}	-0.2
b_C	0.25
b_R	0.5
$b_{C\text{-add}}$	0
$b_{R\text{-add}}$	0.2

In each simulation there was an equal number of subjects in each arm and vaccination history group. Baseline log-titres were simulated from $N(3.7, 1)$ which produced a distribution representative of the baseline titre data of published studies. The error term was sampled from $N(0, 1)$ which produces post-vaccination titre distribution representative of published studies.

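### Section 13.4.2 reads the QIV-R > QIV-C > QIV-E trend from the signs of two estimates and does not tie it to the t-tests it already plans for the same two steps

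*Combined protocol and SAP*

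**What the plan says.** Section 6.2.1 lists the ordering of the three vaccines as an outcome of Secondary Objective 1, first for post-vaccination titre ("Post vaccination trend in GMT QIV-R > QIC-C > QIV-E") and then for seropositivity, fold rise and seroconversion.

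Section 13.4.2 sets out regression models for fold rise, seropositivity and seroconversion, with QIV-E as reference. For each it plans t-tests of QIV-R and QIV-C against QIV-E "as well as the difference in those effects". These tests cover both steps of the ordering: QIV-C against QIV-E, and QIV-R against QIV-C.

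The section then turns to the trend: "The trend will be determined using the estimate of the effect of the cell vaccine", together with the corresponding estimate for QIV-R. The expected pattern is described by sign alone. The QIV-C estimate is to be positive, and "the difference of estimates of the effect of recombinant and cell vaccines should be positive". No test, interval, level or sidedness is attached, and the t-tests are not mentioned again. No other section supplies a criterion.

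**The concern.** The three-step ordering is what Secondary Objective 1 asks about, and the plan says how it will be determined. A rule that needs only two positive estimates takes no account of their uncertainty. It can show a complete ordering when one step, or both, is absent.

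The more important case is the one-step truth. QIV-R contains 45 µg of each antigen against 15 µg in the other two vaccines (sections 7.4.1 to 7.4.3), so QIV-R alone could be better while QIV-C and QIV-E are alike. A sign rule would then place QIV-C above QIV-E about as often as a coin toss. A cell-over-egg benefit could be reported that the trial's own t-test does not support. The rule applies to 3 modelled outcomes × 4 antigens = 12 combinations.

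**Working it through.** **Inputs.** Allocation is 1:1:1 within stratum (section 9.2). Vaccination history is a covariate in all models (13.4). There are 60 participants per arm per history group, about 55 after attrition (13.2). From 13.3: baseline log-titre N(3.7, 1), baseline slope 0.8, prior-vaccination effect -0.2, error N(0, 1), b_C = 0.25, b_R = 0.5, and an extra 0.2 for QIV-R in the frequently vaccinated. Titres are grouped into two-fold intervals and set to midpoints, with values below 10 set to 5.

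**The plan's own figure.** The plan gives no operating characteristic for the trend rule. The nearest figure is the simulated power for b_R = 0.5. Re-running the 13.3 simulation at 55 per arm per history gives 0.805 one-sided and 0.702 two-sided, against the stated 0.810 and 0.712. At 60 it gives 0.823 and 0.736, against 0.832 and 0.741. The simulation model is therefore reproduced closely enough to use.

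**All vaccines equal, fold rise.** With equal arms the two step estimates, C - E and R - C, share the QIV-C mean with opposite sign, so their correlation is -0.5. Then

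P(both > 0) = 1/4 + asin(-0.5)/(2π) = 1/4 - 1/12 = 1/6 = 0.167.

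This does not depend on the standard deviation or the sample size. Simulation gives 0.164 to 0.167.

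**Only QIV-R better, by 0.5, fold rise.** The fold rise has variance (0.8 - 1)² × 1 + 1 = 1.04, so SD 1.02. With 110 per arm (55 in each history group), the standard error of a step is 1.02 × √(2/110) = 0.1375. The R - C step is then 0.5/0.1375 = 3.64 standard errors above zero and is almost always positive (probability 0.9999). The C - E step is positive with probability 0.5. Jointly this is about 0.50; simulation gives 0.495 to 0.499.

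**The plan's effects, fold rise.** Averaged over history, the steps are 0.25 and 0.25 + 0.2/2 = 0.35, or 1.82 and 2.55 standard errors. The sign pattern then appears in about 0.96 of trials before titre grouping, and in 0.946 to 0.957 in simulation.

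**Simulation results.** The runs used 54, 55 and 60 per arm per history, with 10,000 to 20,000 runs per case. Ranges are over the three sizes. "Both tests" below means that both steps are positive and significant.

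| Outcome and truth | Signs only | Both tests, one-sided 5% | Both tests, two-sided 5% |
|---|---|---|---|
| Fold rise, all equal | 0.164-0.167 | at most 0.0001 | at most 0.0001 |
| Fold rise, only QIV-R +0.5 | 0.495-0.499 | 0.041 | 0.015-0.018 |
| Fold rise, plan effects | 0.946-0.957 | 0.336-0.404 | 0.189-0.237 |
| Seroconversion, only QIV-R +0.5 | 0.459-0.473 | 0.025-0.028 | 0.008-0.009 |
| Seroconversion, plan effects | 0.852-0.880 | 0.151-0.179 | 0.056-0.080 |
| Seropositivity, only QIV-R +0.5 | 0.452-0.458 | 0.013-0.016 | 0.003-0.004 |
| Seropositivity, plan effects | 0.784-0.803 | 0.067-0.082 | 0.018-0.028 |

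When all vaccines are equal, the sign pattern for the two binary outcomes appears in about 13-15% of trials. This is below 1/6 because tied proportions count as no trend. The both-tests figures when only QIV-R is better stay below 5% because one of the two tests is then of a true null.

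**The case against.** The best reply is that the plan does not say positive signs are enough. The trend paragraph directly follows the planned t-tests, uses the same estimates, and describes the direction of an expected trend. The objective is phrased as one of estimation, is secondary, and carries no alpha. On that reading the signs are a description with p-values beside them. The 1/6 is then simply the chance that three equal arms fall in one particular order out of six. Read together with the planned QIV-R versus QIV-E test (two-sided 5%), the pattern appears in only about 2% of all-equal trials. Requiring both step tests would also leave many true orderings unconfirmed.

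Much of this stands. A descriptive reading is open, and the power cost is real. But the plan says the trend is determined from the estimates, and nothing in it says the result is descriptive only. Pairing the pattern with the QIV-R versus QIV-E test also gives no protection when only QIV-R is better, because the pattern still appears in about 49% of trials.

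Three stronger readings are tempting and not supported:
- A reader might infer that the steps of the ordering go untested. Section 13.4.2 plans t-tests of both.
- A reader might call 1/6 the trial's type I error rate. No confirmatory claim or error level is attached to this objective, and the figure applies only if the sign pattern is reported as the result.
- A reader might extend the point to the titre analysis. Section 6.2.1 lists a titre trend and 13.4.5 refers to how "post-vaccination log-titres and seropositivity are compared in objective 1", yet 13.4.2 sets out no such titre comparison. That is a separate matter of missing detail.

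**Conclusion.** The concern holds in a limited form. As written, the trend criterion is the sign of two estimates, with no link to the tests of the same two steps. If it is followed literally, for fold rise the full ordering appears in about 1 in 6 trials with no vaccine differences, and in about half of trials with no difference between QIV-C and QIV-E and QIV-R better by 0.5. Requiring both planned tests lowers the second figure to about 4% (one-sided 5%) or 2% (two-sided 5%).

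The 1/6 rests only on equal arms and roughly symmetric estimates. The other simulated figures apply the A(H3N2) design values of 13.3, because the documents give none for the other antigens; for A(H1N1) and B they are illustrative. The plan should be clarified before analysis. The primary test and the sample size are unaffected.

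**What to change.** Replace the trend paragraph of 13.4.2 with wording to this effect: for each outcome and antigen, the contrasts QIV-C minus QIV-E and QIV-R minus QIV-C are reported with confidence intervals; the pattern of signs is descriptive; the full ordering is stated as a finding only where the t-tests already planned for both steps are significant in the expected direction. Give the level and sidedness, which 13.4.2 does not state; the one-sided 5% in 13.2 is given for sizing the primary comparison.

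This takes one or two sentences, with no new data and no new model. The price is power. Under the plan's own A(H3N2) effects, a true ordering would be confirmed in about 34-40% of trials for fold rise (19-24% two-sided), 15-18% for seroconversion (6-8% two-sided) and 7-8% for seropositivity (2-3% two-sided). The binary outcomes would therefore mostly stay descriptive, and the plan should say so in advance. If the sponsor intends description only, stating that and reporting the intervals is enough.
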